3.11. Substance Use

History of tobacco, alcohol use (never, current, former) and drug abuse (both illegal and prescription) will be collected during the Screening Visit. The following information will be recorded:

- Type of substance (Alcohol/Tobacco/ Drug abuse)
- History of usage (Never/Currently/Former)
- Number of years the product was used (for current or former users)
- Stop date of using the product (for former users)

3.12. Prior/Concomitant Medications and Procedures

3.12.1. Prior Medications

The start and stop date, dose, unit, frequency, route of administration, and indication for all prior medications (taken within the 30 days prior to the Screening Visit) and nondrug therapies (eg, blood transfusions, oxygen supplementation, physical therapy, etc) received will be recorded.

3.12.2. Concomitant Medications

The start and stop date, dose, unit, frequency, route of administration, and indication for all concomitant medications taken from the Screening Visit through the EOS (Day 57) Visit, including oral and topical analgesics/anesthetics before study intervention injection, and nondrug therapies (eg, blood transfusions, oxygen supplementation, physical therapy, nutritional supplements, vitamins, vaccinations, etc) received will be recorded.

3.12.3. Prohibited Medications

The following medications are prohibited during the study:

- Opioids (eg, codeine, heroin, hydrocodone, hydromorphone, morphine, oxycodone) 2 weeks prior to the screening visit and during the study period.
- Anticoagulants (warfarin, heparin, direct thrombin inhibitors, Factor Xa inhibitors) and antiplatelet agents (aspirin > 150 mg/day and P2Y₁₂ inhibitors, such as

clopidogrel) from 7 days before the Day 1 Visit through the EOS (Day 57) Visit as these medications can cause additional bruising. However, the use of aspirin ≤ 150 mg per day will be permitted.

- Injectable anesthetic use in or around the plantar nodule targeted for treatment is prohibited from the Day 1 Visit through the EOS (Day 57) Visit.
- Use of an investigational drug during the study

If any prohibited medication is taken during the study, all pertinent information will be recorded. The designated study medical monitor must be informed immediately so the sponsor may determine whether the participant can continue in the study.

3.13. Adverse Events

All adverse events (AEs) and serious adverse events (SAEs) will be collected by the investigator from the time of signing the informed consent through the EOS Visit (Day 57), if eligible. This will include any AEs that are ongoing at the time of completion/termination of the study. Participants who request to discontinue from the study will be asked to complete the 28-day post treatment Safety Follow-up Visit (or phone call if a visit is not possible) to determine the status of any ongoing AEs/SAEs or the occurrence of any new AEs/SAEs.

3.13.1. Adverse Events Definition

An AE is any unfavorable or unintended change in body structure (signs), body function (symptoms), laboratory result (eg, chemistry, ECG, X-ray, etc), or worsening of a preexisting condition associated temporally with the use of the study intervention whether or not considered related to the study intervention. Note: Any medical condition or laboratory abnormality already present at screening or baseline should be reported as medical history. If the medical condition present at baseline changes in severity or seriousness at any time during the study, it should be reported as an AE. AEs will be captured once a participant has signed the informed consent. AEs include:

- Changes in the general condition of the participant
- Subjective symptoms offered by or elicited from the participant
- Objective signs observed by the investigator or other study personnel
- All concurrent diseases that occur after the start of the study, including any change in severity or frequency of pre-existing disease
- All clinically relevant laboratory abnormalities or physical findings that occur during the study

A TEAE is any condition that was not present prior to treatment with study intervention but appeared following treatment, was present at treatment initiation but worsened during treatment, or was present at treatment initiation but resolved and then reappeared while the individual was on treatment (regardless of the intensity of the AE when the treatment was initiated)

3.13.2. Serious Adverse Events

SAEs are AEs that meet any of the following criteria:

- Results in death
- Life-threatening event
- Results in or prolongs an inpatient hospitalization
- Results in permanent or substantial disability
- Is a congenital anomaly or birth defect
- Any important medical event that may jeopardize the participant or may require medical intervention to prevent one of the outcomes listed above

3.13.3. Adverse Events of Special Interest

AESIs are AEs that for meet any of the following criteria:

- Any severe hypersensitivity reactions.
- Plantar fascial tears.

All AESIs will be evaluated for seriousness and severity.

3.13.4. Assessment of the Severity of Local Injection Site Reactions

Based on clinical assessments, investigators should classify and assess the severity of local injection site reactions during the study according to Table 18. The table does not comprise a comprehensive list of injection site reactions. For TEAEs not included, refer to the CTCAE Version 5 for a more comprehensive list of events. Local injection site reactions will be reported as TEAEs in the eCRF.

Table 18: Assessment and Grading of the Severity of Injection Site Reactions

Local Reaction to Study Intervention	Mild (Grade 1)	Moderate (Grade 2)	Severe (Grade 3)	Potentially Life Threatening (Grade 4)
Pain/Pain in extremity	Mild Pain	Moderate pain; limiting instrumental ADL	Severe pain; limiting self-care ADL	
Tenderness	Mild discomfort to touch	Discomfort with movement	Significant discomfort at rest	
Erythema/Redness ^a	2.5 – 5 cm	5.1 – 10 cm	> 10 cm	Necrosis or exfoliative dermatitis
Induration/Swelling ^b	2.5 – 5 cm and does not interfere with activity	5.1 – 10 cm or interferes with activity	> 10 cm or prevents daily activity	Necrosis
Pruritus, itchiness	Mild or localized; topical intervention indicated	Widespread and intermittent; skin changes from scratching (eg, edema, papulation, excoriations, lichenification, oozing/crusts); oral intervention indicated; limiting instrumental ADL	Widespread and constant; limiting self-care ADL or sleep; systemic corticosteroid or immunosuppressive therapy indicated	

Table 18: Assessment and Grading of the Severity of Injection Site Reactions (Continued)

Local Reaction to Study Intervention	Mild (Grade 1)	Moderate (Grade 2)	Severe (Grade 3)	Potentially Life Threatening (Grade 4)
Localized edema	Localized to dependent areas, no disability or functional impairment	Moderate localized edema and intervention indicated; limiting instrumental activities of daily living	Severe localized edema and intervention indicated; limiting self-care activities of daily living	
Bruising, Contusion, Ecchymosis	Localized or in a dependent area	Generalized		
Hemorrhage	Mild symptoms; intervention not indicated	Moderate symptoms; intervention indicated	Transfusion indicated; invasive intervention indicated; hospitalization	Life-threatening consequences; urgent intervention indicated
Hematoma	Mild symptoms; intervention not indicated	Minimally invasive evacuation or aspiration indicated	Transfusion; invasive intervention indicated	Life-threatening consequences; urgent intervention indicated
Skin laceration	Observation only; topical intervention indicated	Bedside local care indicated	Operative intervention indicated	Life-threatening consequences
Injection site lymphadenopathy	Local lymph node enlargement	Localized ulceration; generalized lymph node enlargement		
Injection site reaction	Tenderness with or without associated symptoms (eg, warmth, erythema, itching)	Pain; lipodystrophy; edema; phlebitis	Ulceration or necrosis; severe tissue damage; operative intervention indicated	Life-threatening consequences; urgent intervention indicated
Plantar fascial tear/rupture	Asymptomatic or mild symptoms; clinical or diagnostic observations only; intervention not indicated	Moderate; Minimal or noninvasive intervention indicated	Severe or medically significant but not immediately life-threatening; Invasive intervention indicated	

Source: Adapted from the National Cancer Institute (NCI) Common Terminology Criteria for Adverse Events (CTCAE) Version 5 and FDA Guidance for Industry. Toxicity Grading Scale for Healthy Adult and Adolescent Volunteers Enrolled in Preventive Vaccine Clinical Trials September 1997.

1.1.1. Anaphylaxis

Anaphylaxis is a serious allergic reaction that is rapid in onset and may cause death. To identify individuals experiencing such a reaction, use the criteria provided by Sampson et al (2006) in [Table 19](#). Anaphylaxis will be reported as SAE in the eCRF.

Table 19: Clinical Criteria for Diagnosing Anaphylaxis

Anaphylaxis is highly likely when any 1 of the following 3 criteria are fulfilled:		
1. Acute onset of an illness (minutes to several hours) with involvement of the skin, mucosal tissue, or both (eg, generalized hives, pruritus or flushing, swollen lips-tongue-uvula) AND AT LEAST ONE OF THE FOLLOWING 
 Respiratory compromise (eg, dyspnea, wheeze-bronchospasm, stridor, reduced peak expiratory flow, hypoxemia) Reduced blood pressure or associated symptoms of end-organ dysfunction (eg, hypotonia [collapse], syncope, incontinence) 		
2. Two or more of the following that occur rapidly after exposure to collagenase or any other excipient of EN3835 for that participant (minutes to several hours): 
 Involvement of the skin-mucosal tissue (eg, generalized hives, itch-flush, swollen lips-tongue, uvula) Respiratory compromise (eg, dyspnea, wheeze-bronchospasm, stridor, reduced peak expiratory flow, hypoxemia) Reduced blood pressure or associated symptoms (eg, hypotonia [collapse], syncope, incontinence) Persistent gastrointestinal symptoms (eg, crampy abdominal pain, vomiting) 		
3. Reduced blood pressure after exposure to collagenase or any other excipient of EN3835 for that participant (minutes to several hours): 
 Adults: systolic blood pressure of less than 90 mm Hg or greater than 30% decrease from that person's baseline 		

3.14. Clinical Safety Laboratory Tests

Clinical laboratory tests will be performed by a designated central laboratory as per Table 20. Blood and urine samples will be collected for testing clinical laboratory parameters at Screening and the Day 57 Visit. Any new clinically significant laboratory abnormality observed, will be considered as an AE or SAE as appropriate.

Table 20: Change Clinical Safety Laboratory Parameters

Hematology	Biochemistry	Urinalysis
Hemoglobin	Glucose	Glucose
Hematocrit	Sodium	Protein
Red blood cell	Potassium	Specific gravity
White blood cell (WBC)	Calcium	pH
Platelets	Chloride	Ketones
WBC Differential	Carbon dioxide (CO ₂)	Bilirubin
Prothrombin time (PT)/International Normalized Ratio (INR)	Blood urea nitrogen	Urobilinogen
	Creatinine	Nitrite
	AST	Blood ^a
	ALT	Leukocytes ^a
	Gamma-glutamyl transferase (GGT)	
	TBL (direct bilirubin reflex if elevated)	
	Albumin	
	Alkaline phosphatase (ALP)	
	Total protein	

^a Microscopic examination will be performed if blood or leukocytes are detected.

3.15. Pregnancy Test

All female participants of childbearing potential will have serum and/or urine pregnancy tests at the time points outlined in the SoA (Table 2). Urine pregnancy tests will be provided by the central laboratory to the sites. Results must be available prior to protocol mandated study treatment.

A positive urine pregnancy test at any time will be confirmed with a serum pregnancy test. Any female participant that becomes pregnant during the study will immediately be discontinued from treatment but will continue to be followed as described in Section 8.3.5 of the study protocol.(1)

For all female participants of childbearing potential, the participant's agreement to use contraception throughout their study participation (Screening Visit through Day 57/EOS Visit), will be documented.

3.16. Height, Body Weight and Body Mass Index

Height and body weight measurements will be collected at the Screening Visit. Body Mass Index (BMI) will be calculated using the height and weight at the Screening Visit.

3.17. Vital Signs

Vital signs measurements include systolic and diastolic blood pressure, respiratory rate, pulse, and body temperature will be collected after the participant has been sitting for 5 minutes in the seated position.

Vital signs measurements will be collected at all scheduled visits as per the SoA (Table 2). On the day that study intervention will be administered, vital signs measurements will be collected in a supine position prior to injection, at 15 (± 5) and 30 (± 5) minutes post injection.

The investigator will review all vital sign values for clinical significance. Any clinically significant abnormality observed in a vital sign will be considered as an AE or SAE as appropriate.

3.18. Physical Examination

A complete physical examination (by body system) will be performed at the time points outlined in the SoA (Table 2). This evaluation may include an examination of the head, eyes, ears, nose, throat, neck (including thyroid), cardiovascular system (including assessment of heart, peripheral pulses, presence or absence of edema), lungs, abdomen (including liver and spleen, bowel sounds), lymph nodes, musculoskeletal system (including spine, joints, muscles) neurological system (including cranial nerves, reflexes, sensation, strength), skin, extremities, and other conditions of note.

Physical examination findings will be recorded as normal, abnormal, or not done as not standard of care.

Any clinically significant abnormality in physical examination observed will be considered as an AE or SAE as appropriate.

3.19. Immunogenicity

Immunogenicity variables include binding anti-AUX-I /anti-AUX-II antibodies (ie, anti-drug antibodies) and neutralizing antibody results.

Serum Samples will be collected at Day 1 and at the Day 57 will be tested for binding anti-AUX-I and anti-AUX-II antibodies. If the participant tests positive for anti-AUX-I and anti-AUX-II antibodies, testing for neutralizing antibodies will be conducted.

4. STUDY PARAMETERS

4.1. Participant Disposition

A participant is considered to have completed the study if the participant has completed the EOS Visit. The EOS Visit (Day 57) is defined as the completion of the final assessment for the last participant enrolled in the study. All participants are expected to remain in the study until Day 57, regardless of whether they receive 1 or 2 treatments.

The study completion date is defined as date the final participant was examined or received an intervention for purposes of final collection of data for the primary and secondary outcome measures and adverse events (eg, last participant's last visit or 28-day follow-up Safety Visit). This study completion date applies whether the clinical trial concluded according to the pre-specified protocol or was terminated.

Participants who discontinue/withdrawal from the study after dosing will be encouraged to complete all remaining study visits and evaluations and provide any additional follow-up information required by the study, unless the participant specifically indicates that they will not participate in any further evaluations.

All EOS/ET procedures will be conducted as detailed in the SoA ([Table 2](#)). The reason and date for early withdrawal will be recorded in the eCRF.

Screen failures are defined as participants who consent to participate in this study but are not randomized. A participant who is a screen failure may be rescreened with approval of the sponsor. Participants may be rescreened only once and the reason for the rescreen failure will also be recorded if any participant failed rescreening. The participant must repeat all screening procedures. The period from the start of rescreening related procedures to injection of study intervention must not exceed 28 days. Participants who were in screening (those who had completed or were in the process of screening) for the study at the time of any COVID-19 interruption, but who had not been dosed with study intervention, may be rescreened. The need to repeat screening assessments will be determined on an individual basis.

4.2. Demographics and Baseline Characteristics

Demographics and baseline characteristics include the following parameters in Table 21.

Table 21: Demographic and Baseline Characteristics

Continuous Parameter	Categorical Parameter
Age (years)	Gender
Height (cm)	Race
Body weight (kg)	Ethnicity
BMI in kg/m ²	Report of alcohol and tobacco use 
 Alcohol use (Never, Current, and Former) Tobacco use (Never, Current, and Former)
Nodule Size (Caliper measurements)	Affected Foot 
 Left Right Both

Table 21: Demographic and Baseline Characteristics (Continued)

Continuous Parameter	Categorical Parameter
Nodule Hardness (Durometer measurements)	Nodular Consistency 
 • Hard • Firm Throughout • Moderately Firm • Soft • Non-palpable
FFI Scores at baseline 
 • Total Pain Subscale Score (by orthotics use and overall) • Total Difficulty Subscale Score • Total Activity Limitation Subscale Score • Total Combined (Pain & Difficulty) Score • Total Composite Score 	Total Number of Nodules Treated 
 • 1 • 2 • 3 • 4 • >4
Pain Intensity Numerical Rating Scale	Nodule Size Category 
 • Up to 2 cm • >2 cm to ≤4 cm • >4 cm

4.3. Protocol Deviations

Protocol deviations will be identified and documented prior to database lock. Protocol deviations will be derived from the eCRF data, electronic vendor data, and from the clinical monitoring reports. All deviations from these sources will be reconciled and duplicate deviations will be removed. When a deviation is both found in the database and in clinical monitoring reports, in most cases the text of the deviation from the database will be retained. The exception to this rule will occur if the deviation from the monitoring report provides important information not found in the database.

Possible protocol deviations include, but are not restricted to the following types:

- Ineligible participant/study entry criteria not satisfied
- Informed consent not completed correctly
- Non-compliance with study treatment
- Prohibited medications/procedure
- Visit/procedure missing or out of window

The Endo study team will provide final protocol deviation assignments and classify them as either important or not important during protocol deviation review meetings held throughout the study and prior to the database lock.

All study assessments conducted outside of the allowed windows outlined in the SoA ([Table 2](#)) due to a COVID-19 interruption will be documented as a protocol deviation. COVID-19 will be recorded as the reason for these out-of-window assessments.

4.4. Prior/Concomitant Medications/Procedures

All medications will be coded using the World Health Organization (WHO) Drug Dictionary, by active ingredient and WHO anatomical therapeutic chemical (ATC) classification of ingredients.

Any prior medication/procedure taken/done prior to first injection (Day 1) will be reported as prior medication/procedure.

A concomitant medication/procedure is any medication/procedure taken/done on or after first injection (Day 1) until the EOS Visit or the medication/procedure which were ongoing on Day 1.

4.5. Prior Plantar Fibromatosis Treatment

Prior plantar fibromatosis treatment will be obtained from the prior/concomitant and/or prior concomitant procedure pages of the eCRF. If on either of these pages a medication or procedure is reported with the indication ‘Plantar Fibromatosis’ prior to screening, then the medication or procedure will be considered a prior plantar fibromatosis treatment.

All plantar fibromatosis treatment procedures will also be classified. The classification will be reviewed and approved by the study medical monitor. Any plantar fibromatosis treatment used on or after screening will be noted and reported as a protocol deviation.

4.6. Nodule Assessments

4.6.1. Nodular Consistency of the Selected Nodule

The investigator will classify the nodule as “hard”, “firm throughout”, “moderately firm”, “soft” or “non-palpable” at scheduled visits as per the SoA ([Table 2](#)). All nodule level assessment will be captured in the eCRF.

A participant-level responder is defined as a participant with at least 1-level reduction in nodular consistency from baseline for any treated nodule at follow-up visits. The corresponding baseline value will be used as a controlling factor for the responder analyses.

A foot-level responder is defined as a participant with at least 1-level reduction in nodular consistency from baseline for any treated nodule in that foot at a follow-up visit. The corresponding baseline value will be used as a controlling factor for the responder analyses.

A nodule-level responder is defined as a treated nodule with at least 1-level reduction in nodular consistency from baseline at a follow-up visit. The corresponding baseline value will be used as a controlling factor for the responder analyses.

For participant level classification of nodule in demographic/baseline characteristics table and listing, worst case approach will be used.

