6.2. Participant Exclusion Criteria

A participant is ineligible for study participation if the participant meets any of the following criteria:

Medical Conditions:

1. Has the presence of non-plantar fibromatosis-related nodules on the affected foot/feet (eg, neurofibroma, rhabdomyosarcoma, liposarcoma, neurilemmomas, rheumatoid nodules, desmoid tumors, or malignant soft tissue lesions of the foot or ankle).
2. Has any musculoskeletal, neuromuscular, neurosensory, other neurological or related disorder that affects the participant's use of his or her feet and/or would impair his/her completion of study assessments as determined by the investigator.
3. Has the presence of soft (or not hard/firm) plantar fibromatosis nodule on either foot.
4. Has ≥ 5 plantar fibromatosis nodules (for bilateral and unilateral plantar fibromatosis).
5. For bilateral plantar fibromatosis:
 - Has > 2 nodules per foot OR
 - Has any nodules > 4 cm
6. For unilateral plantar fibromatosis:
 - Has > 3 nodules OR
 - Has ≥ 2 nodule that are > 2 cm each.
7. Has a known systemic allergy to collagenase or any other excipient of EN3835.
8. Has a known bleeding disorder which would make the participant unsuitable for enrollment in the study (see Exclusion Criterion #16).
9. Has a clinically significant laboratory abnormality or any laboratory test results meeting any of the following criteria:
 - a. alanine aminotransferase (ALT) $\geq 3 \times$ upper limit of normal (ULN)
 - b. total bilirubin (TBL) $\geq 2 \times$ ULN ($> 35\%$ direct bilirubin)
 - c. aspartate aminotransferase (AST) $\geq 3 \times$ ULN
 - d. international normalized ratio (INR) > 1.5
10. Has concurrent diseases that might interfere with the conduct of the study, confound the interpretation of the study results, or endanger the participant's well-being, (eg, evidence or history of malignancy other than excised basal-cell carcinoma) or any significant hematological, endocrine, cardiovascular, respiratory, renal, hepatic, or gastrointestinal disease). If there is a history of such disease but the condition has been stable (defined as not requiring significant change in therapy or hospitalization for worsening disease) for more than 1 year and is judged by the investigator not to interfere with participation in the study, the participant may be included, with the documented approval of the medical monitor.

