9.1.1.2. Consistency of the Selected Nodule

At the time points listed in the Schedule of Assessments, the investigator or qualified designee will palpate the selected nodule, determine the consistency of the nodule, and classify the nodule. For the first treatment, only hard, firm throughout, or moderately firm, palpable fibrous nodules will be treated. For the second treatment, nodules previously treated on Day 1 that remain palpable and are either hard, firm throughout, moderately firm, or soft) are eligible for Treatment 2. All efforts should be made to ensure the same investigator is performing these assessments for each participant. The nodule consistency scale is classified as,

4: Hard

3: Firm Throughout

2: Moderately Firm

1: Soft

0: Non-palpable.

Additional information on the classification of the nodule is provided in the Study Operations Manual.

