Exploratory	The difference in the proportion of participants treated with EN3835 or placebo reporting Minimal Improvement (+1), Much Improvement (+2), and Very Much Improvement (+3) on the activity limitation subscale of the PGIC scale, a 7 point scale ranging from -3 (“Very Much Worse”) to +3 (“Very Much Improvement”) on Days 15, 29, 43, and 57.	Cochran-Mantel-Haenszel method (mITT)			
Exploratory	The difference between EN3835 and placebo in the mean change from Baseline (Day 1) to Day Days 15, 29, 43, and 57 on the Pain Intensity NRS, ranging from 0 (“None”) to 10 (“Worst Pain Imaginable”) with EN3835 vs placebo.	MMRM based on (Observed Data) (mITT)			
Exploratory	The difference in the proportion of participants treated with EN3835 or placebo reporting to be “Satisfied” (+1) and “Very Satisfied” (+2) on the Subject Satisfaction With Treatment Scale, a 5-point scale ranging from -2 (“Very Dissatisfied”) to +2 (“Very Satisfied”) on Days 15, 29, 43, and 57.	Cochran-Mantel-Haenszel method (mITT)			
Exploratory	The difference between EN3835 and placebo in the mean change from Baseline (Day 1) to Day Days 15, 29, 43, and 57 on the activity limitation subscale (total score on 3 items) of the FFI, ranging from 0 (“Never”) to 4 (“Always”).	MMRM based on (Observed Data) (mITT)			
Exploratory	The difference between EN3835 and placebo in the mean change from Baseline (Day 1) to Days 15, 29, 43, and 57 on the difficulty subscale (total score on 9 items) of the FFI, ranging from 0 (“No Difficulty”) to 4 (“A Lot of Difficulty”).	MMRM based on (Observed Data) (mITT)			

Table 27: List of Analyses Performed on All Efficacy Endpoints (Continued)

Endpoint (Primary/ Secondary /Exploratory)	Endpoint	Primary analyses	Subgroup Analyses	Sensitivity Analyses	Supportive Analyses
Exploratory	The difference between EN3835 and placebo in the mean change from Baseline (Day 1) to Days 15, 29, 43, and 57 in the nodule size of the treated nodules by caliper measurements.	MMRM based on (Observed Data) (mITT)			Nodule level analyses - MMRM (Observed Data) (mITT)
Exploratory	The difference between EN3835 and placebo in the change in nodule consistency from Baseline (Day 1) to Days 15, 29, 43, and 57 as determined by the number of participants with a soft or non-palpable consistency at Day 57.	Cochran-Mantel-Haenszel method (mITT)			Nodule level analyses: Cochran-Mantel-Haenszel method (mITT)

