7.6.3.2. Key Secondary Endpoint 2: Clinician Global Impression of Change Scale

7.6.3.2.1. Key Secondary Endpoint 2: Primary Analyses

The 2nd key secondary estimand is defined by the following:

- **The *secondary* clinical question of interest is:** In participants with plantar fibromatosis, what is the difference in the proportion of EN3835-treated participants and those receiving only placebo reporting “Minimally Improved” (+1) “Much Improved” (+2) or “Very Much Improved” (+3) on CGIC, a 7-point scale ranging from –3 (“Very Much Worse”) to +3 (“Very Much Improvement”) at Day 57 between EN3835 and placebo, regardless of discontinuation of study intervention?
- **Treatment condition:** Randomized study intervention (EN3835 or placebo)
- **Target Population:** Adult participants with plantar fibromatosis who are included in the ITT Population.
- **Variable (Endpoint) of interest:** Difference in the proportion of participants reporting a response on the CGIC, a 7-point scale ranging from –3 (“Very Much Worse”) to +3 (“Very Much Improvement”) at Day 57
- **Treatments being compared:** The difference in proportion of participants reporting a response on the CGIC at Day 57 will be compared between EN3835 and placebo.
- **Intercurrent Event:** The treatment policy strategy will be adopted for the analyses.
 - Any new or change in concomitant treatment will not be adjusted for primary analyses.
 - Early withdrawal from the study is the potential intercurrent event that could occur. All participants who withdraw early from the study will be considered as non-responders. The responder is defined as a participant who reports a score to be “Minimal Improvement”, “Much Improvement” or “Very Much Improvement” on the CGIC at Day 57.
- **Population Level-Summary measure:** The stratum adjusted risk difference, associated 95% CI and p-value will be presented.
- **Method of Analyses:** The difference in proportion of responders between EN3835 and placebo will be analyzed using Cochran-Mantel-Haenszel (CMH) test stratified by total number of nodules at baseline. The stratum adjusted risk difference, associated 95% CI and p-value will be presented using CMH test. The frequency and percentage of responders and 95% CI will be provided based on the Wilson (Score) by treatment group.

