7.6.4.8. Nodule Consistency – Responder Analyses

7.6.4.8.1. Participant Level Analyses: Change in consistency from Baseline to Day 15, 29, 43 and 57 in the Nodule Consistency

The difference in proportion of responders between EN3835 and placebo will be analyzed using CMH test stratified by baseline nodule consistency separately for each visit.

The stratum adjusted risk difference, associated 95% CI and p-value will be presented separately for each visit. The frequency and percentage of responders (Section 4.6.1) and 95% CI will be provided based on the Wilson (Score) by treatment group and visit (ie, Days 15, 29, 43, and 57).

The degree of improvement in nodular consistency will be summarized using frequency and percentages with mean and SD by each treatment group and visit (ie, Days 15, 29, 43, and 57).

A listing of nodule consistency will be provided by participant.

7.6.4.8.2. Nodule Level Analyses: Change in consistency from Baseline to Day 15, 29, 43 and 57 in the Nodule Consistency

The difference in proportion of responders between EN3835 and placebo will be analyzed using CMH test stratified by baseline nodule consistency separately for each visit and each nodule.

The stratum adjusted risk difference, associated 95% CI and p-value will be presented separately for each visit. The frequency and percentage of responders (Section 4.6.1) and 95% CI will be provided based on the Wilson (Score) by treatment group and visit (ie, Days 15, 29, 43, and 57).

The degree of improvement in nodular consistency will be summarized using frequency and percentages with mean and SD by each treatment group and visit (ie, Days 15, 29, 43, and 57) for each treated nodule.

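### The stated nodule-consistency endpoint (soft or non-palpable at Day 57) has no derivation in the SAP, which analyses a one-grade drop in any treated nodule instead

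*SAP*

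**What the plan says.** The consistency objective has two endpoint bullets in Protocol Sections 2.1 and 4 and in SAP Table 1. The first compares arms on the number of participants whose nodules are soft or non-palpable at Day 57. The second is change from baseline in consistency at Days 15, 29, 43 and 57, with no threshold. SAP Table 27 merges the two into one row and keeps the first bullet's criterion: "as determined by the number of participants with a soft or non-palpable consistency at Day 57".

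SAP 4.6.1 defines a different responder: "a participant with at least 1-level reduction in nodular consistency from baseline for any treated nodule". Its nodule-level responder is likewise a drop of one grade or more. SAP 7.6.4.8.1 and 7.6.4.8.2 both point back to it ("The frequency and percentage of responders (Section 4.6.1") and use a "CMH test stratified by baseline nodule consistency separately for each visit".

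Three other provisions matter:
- Protocol 10.3.1.2.4 leaves responder definitions to the SAP.
- SAP 4.7.5 and 4.8.1 combine two feet by the worse rating for satisfaction and for the Clinician Global Impression of Change (CGIC). SAP 7.6.3.2.1 analyses CGIC with a CMH "test stratified by total number of nodules at baseline".
- SAP Table 28 lists one change from protocol, about prior medications.

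**The concern.** A reader of Table 27 would take the reported proportion to be participants whose nodules became soft or disappeared on palpation. Under SAP 4.6.1, a participant whose one hard nodule becomes firm throughout counts as a responder, although that nodule is still in a grade that qualified for treatment on Day 1. With several nodules, one such shift is enough even if the others are unchanged or worse. The rate, risk difference and nominal p-value would then describe an event that the endpoint tables do not name, and the named event would have no result.

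**Working it through.** The documents give no rate, power or sample size for this endpoint, so there is no plan figure to reproduce. Two checks apply.

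**1. Which Day 57 grades qualify.** The scale runs from 4 (hard) through 3 (firm throughout), 2 (moderately firm) and 1 (soft) to 0 (non-palpable). On Day 1, "only hard, firm throughout, or moderately firm, palpable fibrous nodules will be treated" (Protocol 9.1.1.2), so every treated nodule starts at 2, 3 or 4.

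| Baseline grade | Stated endpoint (score ≤ 1) | SAP 4.6.1 (drop ≥ 1) | Drop needed for stated endpoint |
|---|---|---|---|
| 4 hard | 0, 1 | 0, 1, 2, 3 | 3 |
| 3 firm throughout | 0, 1 | 0, 1, 2 | 2 |
| 2 moderately firm | 0, 1 | 0, 1 | 1 |

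Reaching 0 or 1 always implies a drop of at least one grade, so the SAP event contains the stated event. It is strictly wider for two of the three baseline grades and identical for the third.

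**2. Dependence on nodule count.** Protocol 6.2 excludes anyone who "Has ≥ 5 plantar fibromatosis nodules (for bilateral and unilateral plantar fibromatosis". It also limits unilateral disease to three nodules and bilateral disease to two per foot. The count k therefore runs from 1 to 4, and four is possible only in bilateral disease.

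Let p be the chance that one nodule drops a grade or more. The documents give no placebo or rating-noise value, so p = 0.30 is an assumption.

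- Independent nodules: P(any) = 1 − (1 − p)^k. For k = 4, 1 − 0.7⁴ = 1 − 0.2401 = 0.76.
- Correlated nodules (beta-binomial, correlation ρ): with a = p(1 − ρ)/ρ and b = (1 − p)(1 − ρ)/ρ, P(any) = 1 − ∏(b + i)/(a + b + i), i = 0 to k − 1. For ρ = 0.5, a = 0.3 and b = 0.7. For k = 4, 1 − (0.7/1)(1.7/2)(2.7/3)(3.7/4) = 0.505.

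| Rule, p = 0.30 | k = 1 | k = 2 | k = 3 | k = 4 |
|---|---|---|---|---|
| Any nodule, independent | 30% | 51% | 66% | 76% |
| Any nodule, ρ = 0.5 | 30% | 41% | 47% | 51% |
| Any nodule, ρ = 0.8 | 30% | 34% | 36% | 38% |
| All nodules, independent (p^k) | 30% | 9% | 2.7% | 0.8% |

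The any-nodule rate rises with count in every case, much less so when nodules behave alike. An all-nodules rule depends on count too, in the other direction.

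The effect on the treatment difference has no fixed sign. With independent nodules and assumed per-nodule rates of 0.20 and 0.50, the any-nodule difference is 0.30 for one nodule and 0.35 for four. With 0.30 (assumed) and 0.727 (the per-nodule figure for the lowest concentration in EN3835-105, Protocol 3.2.1), it is 0.43 for one and 0.24 for four.

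**The case against.** The protocol expressly delegates responder definitions to the SAP and names nodule consistency among the response rates, so a SAP definition is authorised. The second endpoint bullet is a change from baseline by visit, and a one-grade responder by visit is a reasonable analysis of it. Both points stand. They justify keeping the one-grade analysis and weaken any complaint that rests on Table 28 alone. They do not supply an analysis of the first bullet, and the SAP's own Tables 1 and 27 still state the soft or non-palpable criterion.

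A reader might go further in three ways that the documents do not support.

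- **Bias or false-positive inflation.** Allocation is randomised 1:1, so nodule count balances on average. The endpoint is outside the testing hierarchy (Protocol 10.4, SAP 6.5). The supportive nodule-level CMH does not use the any-nodule rule, although it keeps the one-grade threshold.
- **Most placebo participants responding through rating noise.** Rates near 76% need an assumed 30% per-nodule chance, independence and four nodules. Nodules share a participant and, by intent, an assessor. Protocol 3.1 puts bilateral presentation at 25% of patients. From moderately firm, the stated endpoint is equally open to a one-grade shift.
- **A criterion already at its ceiling.** In EN3835-105, 100% and 87.5% of participants at the two higher concentrations improved by at least one level. In the Retreatment Period at 2.25 mg/mL, the concentration used here, the figure was 81.8%. The study was open-label, began with eight participants per group and had no placebo arm. The protocol does not say that it used the present five-grade scale or an any-nodule rule. A high active rate alone does not show that the arms could not be separated.

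**Conclusion.** The mismatch is established from the text and needs no assumption: the first endpoint bullet is stated in both documents, and neither derives or analyses it. The redacted SAP blocks lie in other sections; SAP Module 2 (table shells and code) is not among the documents and could not be checked.

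The analysed event is two qualifying grades wider for a hard nodule, one wider for a firm-throughout nodule and the same for a single moderately firm nodule. How far this raises response rates cannot be computed, because the documents give neither the baseline grade mix nor a rate for reaching soft or non-palpable. Dependence on nodule count is certain in direction; its size rests on the assumed p and correlation.

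The consequence is a mislabelled exploratory result. It is worth correcting before database lock, and it does not touch the primary result, alpha or sample size.

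**What to change.** 1. In SAP 4.6.1, add a responder defined as consistency score ≤ 1 at Day 57, at nodule level and at participant level, with one stated aggregation rule. Worst treated nodule ≤ 1 is one option. It matches the worst-case handling of CGIC and satisfaction, but the protocol does not say whether any or all nodules must qualify, so it should be labelled as a choice.
2. Use this responder in SAP 7.6.4.8 for the first endpoint bullet. Keep the one-grade responder by visit as the analysis of the second bullet, labelled as such, and split the Table 27 row to match.
3. Present results by number of nodules, or stratify by it as for CGIC, since any and all rules both depend on count. Crossing four counts with three baseline grades gives up to 12 strata, about 172/12 ≈ 14 participants each on average, so adjacent counts may need pooling.
4. If noise rates are quoted in support, give them as assumptions with a correlated range, and cite the 81.8% retreatment figure beside 87.5% and 100%.

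The cost is SAP wording, one extra derived variable from nodule-level data already collected, and response rates that look lower than under the one-grade rule.
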